**List of Definitions**

Term	Definition
EDC	Electronic Data Capture is a computerized system designed for the collection of clinical data in electronic format including the eCRF.
IWRS	Interactive Web-Based Response System that manages randomization, subject enrollment, and drug supply.
Screening Visit (Visit 1)	The day a subject is screened according to the protocol inclusion/exclusion criteria after having provided informed consent. The screening visit may occur on the same day as Visit 2 (Baseline) for this study.
Screened Subject	A subject who has signed informed consent.
Baseline Visit (Visit 2/Day 1)	The day of randomization and the first study product application. The first study product application is done at the site by the subject during the visit.
Subject Number	A unique number assigned to a screened subject. The number consists of the 2-digit unique site number followed by a 3-digit sequential number for each subject in chronological order (e.g., 01-001, 01-002, where the site number is 01 and the first and second screened subject at site 01 are 001 and 002, respectively). The subject number is assigned by clinical sites.
Study product(s)	Investigational products, that include the active and Vehicle products.

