### 4.2 Discussion of Design

The study consists of three phases: Screening (up to 60 days), Treatment (12 weeks) and Follow-Up (4 weeks). In Groups 2 and 4, the randomized investigational products will be applied twice daily for 12 weeks to cover the entire single contiguous 5 cm x 5 cm (25 cm^2) lesional area on the face and/or scalp. In Groups 1 and 3, the randomized active DFD-07 (celecoxib) Cream product will be applied only in the evening, while the Vehicle for DFD-07 Cream will be applied in the morning to keep the blinding between groups.

Subjects in all the groups will undergo a further 4-week treatment-free period from Week 12 to Week 16 (End of Study).

The investigational products will be applied twice daily for 12 weeks to cover the entire lesional area (5 cm x 5 cm) on the face and/or scalp identified by the Investigator for treatment. The dose for the study product will be a maximum of 0.5 g per application to the entire 5 cm x 5 cm area on the face and/or scalp for a maximum dose of 1.0 g per day.

Subject visits are scheduled at Screening (Visit 1), Baseline (Visit 2 - Day 1), and Weeks 4 (Visit 3), 8 (Visit 4), 12 (Visit 5) and 16 (Visit 6). Clinical determinations of efficacy will be conducted based on clinically visible or palpable lesions of AK in the treated areas at Weeks 4, 8, 12 and 16 in comparison to Baseline. Comparisons will be made between the different strengths and dosing regimens of DFD-07 (celecoxib) Cream and Vehicle Cream.

Local cutaneous tolerability will be determined at Visits 2 – 6 for the entire treated area. Other safety assessments include physical examinations (HEENT, lungs, heart, abdomen, skin,

---

neurologic), laboratory assessments, electrocardiogram (EKG), vital signs (blood pressure, pulse rate), urine pregnancy tests, and collection of adverse event data.

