### **6.2 Treatment Regimen**

Subjects will use assigned study product twice daily (i.e. in the morning and in the evening, after any bathing or showering) with approximately 12 hours between applications for 12 consecutive weeks starting from Baseline/Day 1 (Visit 2) during the study visit. After randomization during the Baseline/Day 1 Visit (Visit 2), subjects will apply the first dose of study medication in the Investigator's office under supervision. The area(s) of application must be washed (with an Investigator-approved cleanser) before the study product is applied. Subjects should be instructed to apply a dime size amount of study product to the Investigator identified single contiguous treatment area (5 cm x 5 cm). Subjects will be provided with a diary to record the timing of application of the study medication on a daily basis. Starting with the first application during the Day 1 Visit, all applications will be recorded in the subject diary, which

---

will be checked by the Investigator or designee for compliance and potential safety-related data at Visits 3-6.

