## 6.6 Blinding

### 6.6.1 Method of Blinding

This is a multi-center, randomized, double-blind, parallel group, Vehicle-controlled study. The DFD-07 (celecoxib) Cream and Vehicle Cream are white to off-white in color, and are similar in appearance, smell, and feel. The study medication kits (active and vehicle) will be marked for AM and PM use, so as to ensure blinding of the QD versus BID arms of the study. In the QD arms for the active product, the active product marked PM will be applied in the evening while the vehicle product marked AM will be applied in the morning. Since the active and vehicle product are similar, the study blind is expected to be preserved by this approach.

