### 11.2.2 Per Protocol

The PP population will include all subjects in the ITT population who complete the Week 16 evaluation without any major protocol violations (i.e., any subject or Investigator activity that could have possibly interfered with the therapeutic administration of the treatment or the precise evaluation of treatment efficacy).

Specifically, the PP population will include subjects in the ITT population who meet all of the following criteria:

1. Subject met all inclusion/exclusion criteria.
2. Subject did not take any prohibited concomitant medications during the evaluation period. The concomitant medication usage will be reviewed during the population determination review, remaining blinded to treatment designation, to determine prohibited medication usage that warrants exclusion from the PP population if they met the entry criteria without any protocol violations. This review will take into consideration the timing, duration of treatment with the concomitant medication, and influence on the efficacy and safety assessments prior to deeming a prohibited concomitant medication as a protocol violation that warrants exclusion from PP.
3. Completed the Week 16 visit within the allowed window.
4. Subject was compliant with the dosing regimen. A subject will be considered compliant if the subject applied at least 80%, but no more than 120% of the expected number of applications during the entire treatment period.

Subjects who prematurely discontinue from the study due to documented lack of efficacy, worsening condition, or a treatment-related AE will be included in the PP population. These subjects will be considered failures for all subsequent visits in the analysis of the primary and secondary endpoints of complete and partial clearance. Other than this, no imputations for missing data will be made for the PP populations.

Other additional criteria may be added to the list to accommodate for unforeseen events that occurred during the conduct of the trial that result in noteworthy study protocol violations. These criteria will be documented with appropriate signature at the time subject populations are finalized, prior to database lock.

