4. Subject was compliant with the dosing regimen. A subject will be considered compliant if the subject applied at least 80%, but no more than 120% of the expected number of applications during the entire treatment period.

Subjects who prematurely discontinue from the study due to documented lack of efficacy, worsening condition, or a treatment-related AE will be included in the PP population. These subjects will be considered failures for all subsequent visits in the analysis of the primary and secondary endpoints of complete and partial clearance of AK lesions. Other than this, no imputations for missing data will be made for the PP populations.

Other additional criteria may be added to the list to accommodate for unforeseen events that occurred during the conduct of the trial that result in noteworthy study protocol violations. These criteria will be documented in the Documentation of Statistical Decisions.

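### The Per Protocol compliance rule counts morning and evening applications together, so a once-daily subject can pass with about 61% of active doses, while the twice-daily arm is held to about 80%

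*SAP*

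**What the plan says.** Criterion 4 of the PP definition in SAP 2.2 requires "at least 80%, but no more than 120% of the expected number of applications during the entire treatment period". Protocol 11.2.2, criterion 4, sets the same limits. Neither document divides the count by time of day or by active and Vehicle tube.

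Protocol 6.2 has all subjects apply product morning and evening for 12 weeks. In the once-daily arms (Groups 1 and 3), according to Protocol 6.6.1, "the active product marked PM will be applied in the evening while the vehicle product marked AM will be applied in the morning". Protocol 4.2 gives the reason for the morning tube: Vehicle is applied "while the Vehicle for DFD-07 Cream will be applied in the morning to keep the blinding between groups". In Group 2 (2.5% twice daily) both tubes are active, and in Group 4 both are Vehicle.

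The List of Definitions describes study products as "Investigational products, that include the active and Vehicle products", so a Vehicle application counts as an application. Protocol 6.4 has sites record the number applied and the number missed, and states no split by time of day.

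The PP set is supportive: SAP 2.2 makes ITT the primary efficacy set, and SAP 2.1 asks for efficacy summaries in both. SAP 4.1 lists PP tables for complete clearance, partial clearance, lesion count and local skin reactions.

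**The concern.** A PP analysis is meant to describe subjects who took the treatment broadly as assigned. In Groups 1 and 3 half of the expected applications are Vehicle. Under a pooled count, a full set of morning Vehicle applications can make up for missed evening active ones. The rule then says little about how much celecoxib a once-daily subject applied, whereas in Group 2 it measures this directly.

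The single objective of the trial is the dose-response relationship, and the first two secondary endpoints compare the once-daily arms with Vehicle. If the PP set tolerates lower active adherence once daily than twice daily, a PP comparison across regimens mixes dose with adherence. Any bias would tend to favour the twice-daily regimen.

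**Working it through.** The documents give no application count for this rule, so there is no figure of theirs to reproduce. The counts below follow from the schedule.

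**Inputs**
- Treatment of 12 weeks = 84 days, two applications a day in every arm (Protocol 6.2).
- Active slot in Groups 1 and 3: evening only (Protocol 4.2, 6.6.1).
- Compliance limits of 80% and 120% of expected applications (SAP 2.2; Protocol 11.2.2).

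**Pooled limits**
- Expected: 2 × 84 = 168, of which 84 are morning and 84 evening.
- Lower limit: 0.8 × 168 = 134.4, so at least 135 (135/168 = 80.4%).
- Upper limit: 1.2 × 168 = 201.6, so at most 201.

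**Lowest active share that passes, all morning applications made and none extra**
- Groups 1 and 3: 135 − 84 = 51 evening applications, so 51/84 = 60.7% of active doses. All 33 misses (168 − 135) are evening ones.
- Group 2: every application is active, so any subject with 135 has 135/168 = 80.4% of active doses, however the misses fall.

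**Sensitivity of the 60.7%**
- The Week 12 window of ±5 days gives 79 to 89 days. At 79 days: 158 expected, 127 needed, (127 − 79)/79 = 48/79 = 60.8%. At 89 days: 178 expected, 143 needed, (143 − 89)/89 = 54/89 = 60.7%.
- With only one application on Day 1: 167 expected, 134 needed, giving 50/83 = 60.2% or 51/84 = 60.7%, depending on which slot is lost.
- Extra morning applications would lower the share further. With 100 morning applications, 35 evening ones reach 135, which is 35/84 = 41.7%. So 60.7% is not an absolute floor.
- The upper limit behaves the same way: 84 morning + 117 evening = 201 passes with 117/84 = 139% of active doses.

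**How extreme the case is.** The documents give no adherence data. For a once-daily subject with 33 misses and no extra applications:
- Even split: (84 − 16.5)/84 = 80.4% of active doses.
- Two evening misses to one morning miss: (84 − 22)/84 = 62/84 = 73.8%.
- All evening: 60.7%.
- If the misses fell at random over the 168 slots (an assumption; hypergeometric), the chance that all 33 are evening ones is about 2 × 10⁻¹², and the chance that active adherence is below 70% (26 or more evening misses) is about 0.0002. Only a subject who habitually skips the evening slot gets near the extreme.

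**With an added evening limit**
- 0.8 × 84 = 67.2, so at least 68. 1.2 × 84 = 100.8, so at most 100.
- Minimum active share kept in Groups 1 and 3: 68/84 = 81.0%.
- 84 evening + 67 morning = 151/168 = 89.9%: kept now and still kept.
- 67 evening + 84 morning = 151/168 = 89.9%: kept now, but excluded under the added limit (67/84 = 79.8%), in every arm.

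**The case against.** **The rule measures the regimen, and the regimen is twice daily.** This stands in part. A reader might infer that the rule is also wrong in the other direction, because a once-daily subject with 84 evening and 50 morning applications (134/168 = 79.8%) is dropped with 100% of active doses. The documents do not support calling that an error. Criterion 4 asks about compliance with the dosing regimen, and the morning Vehicle is part of it in Groups 1 and 3. Nor is Vehicle treated as inert: the sample size assumes 20% clearance on it, and the animal studies in Protocol section 1 attribute local skin effects to non-active components. That subject departed from the assigned regimen and may properly be excluded.

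**The 60.7% subject is a corner case.** This stands as a limit on size. Random misses would almost never produce it. Subjects are blinded and all arms share one schedule, so nothing suggests that evening skipping would differ by arm. What could differ is its consequence, since an evening miss costs a once-daily subject twice the share of active doses that it costs a twice-daily subject.

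**Other clauses catch it.** The PP definition excludes major violations that could have interfered with treatment, Protocol 6.4 has sites ask about missed doses, and criteria can be added before database lock. These permit case-by-case exclusion. They are not a stated morning/evening rule, and this situation can be foreseen now.

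**Little depends on it.** This also stands. ITT is primary, and the tests in SAP 2.6 are each against Vehicle. No PP dose-response test is planned, and SAP 4.2 lists figures for ITT only.

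**Conclusion.** The point holds as a modest one. As written, the PP criterion lets a once-daily subject count as compliant with as few as 51/84 (60.7%) of active doses, against 80.4% in the twice-daily arm. This assumes an 84-day course, one pooled count, all misses in the evening and no extra morning applications. Pooling is inferred from the undivided count, since neither document uses the word, but no other reading is stated.

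The effect is confined to the PP results for Groups 1 and 3 and to any PP reading across doses. A reader might infer that the main efficacy conclusion is at risk. It is not: the primary comparison is ITT, 2.5% twice daily against Vehicle, and both slots hold the same product within each of those arms. Nor do the documents show how many subjects would be affected or by how much an estimate would move. This is a cheap improvement to make before database lock, not a threat to the trial.

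**What to change.** In SAP 2.2 and Protocol 11.2.2, criterion 4, keep the pooled 80-120% limit and add, identically for all four arms, that evening applications must also be 80-120% of the expected evening number (68 to 100 for an 84-day course). Because every kit is labelled for morning or evening use (Protocol 6.1.2), the rule can be applied without treatment codes, before the populations are signed off. Subjects who missed only some morning applications and still meet the pooled limit stay in.

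A full 80-120% limit on each slot would go too far. It would newly exclude a subject with 84 evening and 67 morning applications (89.9% overall).

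Costs: a few lines of text and programming, and separate morning and evening counts. Protocol 6.2 says the diary records timing, but Protocol 6.4 mentions only dates and total applied and missed counts, so the sponsor should confirm that the split can be taken from the diary into the database. The PP set may be slightly smaller in all arms. In Group 2 this includes a subject with 84 morning and 67 evening applications, who has 89.9% of active doses but fails the evening limit. That is the price of one blinded rule for every arm.

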2.3. Subset Analyses

Subgroup analyses will be done based on age (above 65 years vs below 65 years), median age (at or above median age vs. below median age), gender, race, ethnicity, location of treated lesion(s) (on the face and/or scalp) and previous treatment of AK (naïve vs experienced).

2.4. Study Conduct and Baseline Characteristics

2.4.1. Demographics and Subject Baseline Characteristics

Subject demographics and baseline data characteristics will be reported in descriptive summaries by treatment group for the Intention-to-Treat, Per Protocol and Safety populations. Data will also be shown in data listings by treatment group and subject.

Evaluation for significance of the comparisons of the individual baseline characteristics between treatment groups will be performed using an analysis of variance model (for continuous data) or Fisher's exact test (for categorical data).

2.4.2. Extent of Exposure

The extent of exposure to study product will be summarized as the total number of applications, the total number of days the subject was receiving drug (last dose date – first dose date + 1) and the total amount of study product used based on tube weights. The amount of the last dose will be provided based on tube weight before and after treatment. Also, the calculated mean amount of drug used per application will be provided.

2.4.3. Prior and Concomitant Medications

Prior and concomitant medications will be summarized by frequencies and percentages. All medications will be coded using the World Health Organization (WHO) Drug dictionary September 2016 version.

Prior medications will be defined as any medication that started prior to the first day of injection. Concomitant medications will be defined as any medication that starts or is ongoing on or after the first day of injection. A medication may qualify as both a prior and concomitant medication if it started prior to first dose and is ongoing or stopped after the day of dosing.

Medications will be summarized by treatment.

Section 2.10 describes the imputation rules for partial dates. All medications will be presented in a data listing.

2.5. Safety Evaluations

The following safety parameters will be tracked at designated intervals throughout the trial:

- Adverse Events
- Safety and Local Tolerability Evaluation
- Vital signs
- Physical examination
- Electrocardiogram
- Safety Laboratory Tests

2.5.1. Adverse Events (AEs)

Adverse events will be coded using the medical dictionary of regulatory activities (MedDRA Version 19.1) dictionary.

All reported treatment emergent AEs will be summarized by treatment group, the number of subjects reporting events and the no. of AEs reported, system organ class, preferred term, severity, relationship to study product, and seriousness. When summarizing AEs by causality and severity, each subject will be counted only once within a system organ class or preferred term by using the event with the greatest relationship and highest severity within each classification.

Serious adverse events (SAEs) will be summarized by severity and relationship to study product, and SAEs will be listed by subject. In addition, a list of subjects who prematurely discontinued from the study due to an AE will be provided.

All information pertaining to AEs noted during the study will be listed by subject, detailing verbatim term given by the Investigator, preferred term, system organ class, onset date, resolution date, maximum severity, seriousness, action taken regarding study product, corrective treatment, outcome and drug relatedness. The event onset will also be shown relative (in number of days) to date of first administration.

AEs related to study procedures done before study product administration will be provided in a data listing.

2.5.2. Safety and Local Tolerability Evaluation

A safety and local tolerability evaluation will be performed at baseline and each post-baseline visit. This evaluation will include: erythema, edema, weeping/exudate, flaking/scaling/dryness, scabbing/crusting, erosion/ulceration and vesiculation/blistering.

These results will be summarized as frequency and percentages for each evaluation by severity (None, Mild, Moderate and Severe) at each visit in which the evaluation took place.

This information will also be presented in subject data listings.

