#### **7.10.7 Early Withdrawal**

If a subject is withdrawn from the study according to any of the criteria defined in Section 7.6, the following procedures will be performed:

1. Evaluate treatment and protocol compliance and record any deviations. This includes a review of the diary card for number of applications and missed applications.
2. Investigator is to document the number and location of the lesions with in the treatment area and on a grid foil. One copy of the grid foil should be inserted into the subject's source document.
3. Collect vital signs (blood pressure and pulse rate).
4. Perform a physical examination (HEENT, lungs, heart, abdomen, skin, and neurologic).
5. Perform a 12-lead EKG.
6. Collect blood (2/3 tablespoon) and urine for hematology/chemistry/urinalysis safety labs.
7. Conduct a urine pregnancy test for all females of child bearing potential.
8. Collect AE data. This includes a review of the diary card for potential AEs.
9. Update concomitant medications data.
10. Weigh tubes when they are collected.
11. Complete eCRF.

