### **8.2 Recording Adverse Events**

All AEs will be documented including

- Severity (see [8.3.1: Severity](#) for details)
- Start and stop date
- Causality assessment with study medication
- Measures / action taken
- Serious AE (yes/no)

All AEs will be followed-up until resolution or the End of Study Visit and documented in CRF and subject's medical file.

SAEs will be documented in the subject's medical file, the CRF and on the SAE-form. A copy of the SAE form will be emailed or faxed to the Sponsor and filed in the Investigator's File.

Local Reactions in the treatment area will be documented separately. The following local reactions will be assessed and documented:

- a. Erythema
- b. Edema
- c. Weeping/exudate
- d. Flaking/scaling/dryness

- e. Scabbing/crusting
- f. Erosion/ulceration
- g. Vesiculation/blistering

Per definition, all Local Reactions are causally related to the study treatment.

All Local Reactions will be documented including

- Severity
- Start and stop date

The severity of the local reactions is graded as follows:

Grades	Score	Description
None	0	No signs of reaction
Mild	1	Slight signs of reaction
Moderate	2	Definite signs of reaction
Severe	3	Subject discontinues study product due to reaction

The Investigator will record all adverse events, regardless of relationship to study product, on the adverse event CRF. Standard medical terminology should be used when describing adverse events. Whenever possible a diagnosis should be made and recorded on the CRF rather than listing signs and symptoms. Intermittent adverse events can be recorded once. The anatomical location of the adverse event must be specified, when applicable, as well as whether the location is a treatment area. The following information should be recorded on the CRF:

1. Description
2. Start date
3. Stop date or date of death, ongoing, or unknown
4. Severity of the event (see [8.3.1: Severity](#) for details)
5. Study product use continued or not
6. Outcome of the event (recovered/resolved, recovered/resolved with sequelae, not recovered/not resolved, unknown, fatal)
7. Relationship to study product (see [8.3.2: Relationship to Study Product \(Causality\)](#) for details)
8. Indication of whether the event is serious (see [8.3.3: Seriousness](#) for details)
9. Action taken including treatment with concomitant medication

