### 11.5.2 Local Safety Evaluation

Erythema, edema, weeping/exudate, flaking/scaling/dryness, scabbing/crusting, erosion /ulceration and vesiculation/blistering will be summarized by visit.

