1.3.2. Secondary Efficacy Endpoints

The secondary efficacy endpoints for the study are:

1. Proportion of subjects with complete clearance of AK lesions at the End of Study Visit, for DFD-07 (celecoxib) Cream, 2.5% QD compared to Vehicle Cream.
2. Proportion of subjects with complete clearance of AK lesions at the End of Study Visit, for DFD-07 (celecoxib) Cream, 1.25% QD compared to Vehicle Cream.
3. Proportion of subjects with complete clearance of AK lesions at Week 12 in the different treatment groups.
4. Proportion of subjects with complete clearance of AK lesions at Week 8 in the different treatment groups.

5. Proportion of subjects with partial clearance of AK lesions at Week 4, 8, 12, and 16 in the different treatment groups (partial clearance defined as at least a 75% reduction in the number of AK lesions in the treatment area compared to Baseline).
6. Percent change from baseline in AK lesion count at Week 4, 8, 12 and 16 in the different treatment groups.
7. Number and proportion of subjects with local skin reactions in the different treatment groups.

2. Detailed Statistical Methods

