14.2.4.5	Percent Change from Baseline in Actinic Keratosis Lesion Count by Visit – By Gender – Last Observation Carried Forward - ITT Population
14.2.4.6	Percent Change from Baseline in Actinic Keratosis Lesion Count by Visit – By Race – Last Observation Carried Forward - ITT Population
14.2.4.7	Percent Change from Baseline in Actinic Keratosis Lesion Count by Visit – By Ethnicity – Last Observation Carried Forward - ITT Population
14.2.4.8	Percent Change from Baseline in Actinic Keratosis Lesion Count by Visit – By Location of Treated Lesion(s) – Last Observation Carried Forward - ITT Population
14.2.4.9	Percent Change from Baseline in Actinic Keratosis Lesion Count by Visit- By Previous AK treatment – Last Observation Carried Forward - ITT population
14.2.5.1	Percent Change from Baseline in Actinic Keratosis Lesion Count by Visit – Multiple Imputation Method - ITT Population
14.2.5.2	Percent Change from Baseline in Actinic Keratosis Lesion Count by Visit – Multiple Imputation Method - PP Population
14.2.5.3	Percent Change from Baseline in Actinic Keratosis Lesion Count by Visit – Based on Age – Multiple Imputation Method - ITT Population
14.2.5.4	Percent Change from Baseline in Actinic Keratosis Lesion Count by Visit – Based on Median Age – Multiple Imputation Method - ITT Population
14.2.5.5	Percent Change from Baseline in Actinic Keratosis Lesion Count by Visit – By Gender – Multiple Imputation Method - ITT Population
14.2.5.6	Percent Change from Baseline in Actinic Keratosis Lesion Count by Visit – By Race – Multiple Imputation Method - ITT Population
14.2.5.7	Percent Change from Baseline in Actinic Keratosis Lesion Count by Visit – By Ethnicity – Multiple Imputation Method - ITT Population

Table Number	Table title
14.2.5.8	Percent Change from Baseline in Actinic Keratosis Lesion Count by Visit – By Location of Treated Lesion(s) – Multiple Imputation Method - ITT Population
14.2.5.9	Percent Change from Baseline in Actinic Keratosis Lesion Count by Visit- By Previous AK treatment – Multiple Imputation Method - ITT population
14.2.6.1	Proportion of Subjects with Local Skin Reactions by Visit – ITT Population
14.2.6.2	Proportion of Subjects with Local Skin Reactions by Visit – PP Population
14.2.6.3	Proportion of Subjects with Local Skin Reactions by Visit – Based on Age – ITT Population
14.2.6.4	Proportion of Subjects with Local Skin Reactions by Visit – Based on Median Age – ITT Population

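### Secondary endpoint 7 (subjects with local skin reactions) has only by-visit tables; the SAP defines no any-time proportion of subjects and no worst post-baseline grade

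*SAP*

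**What the plan says.** SAP 1.3.2 and Protocol 3.2 list endpoint 7 as "Number and proportion of subjects with local skin reactions in the different treatment groups". Endpoints 1 to 6 each name the End of Study Visit or particular weeks. Endpoint 7 names neither.

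The planned summaries are these:

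- SAP 2.5.2 on timing: "A safety and local tolerability evaluation will be performed at baseline and each post-baseline visit".
- SAP 2.5.2 on presentation: "These results will be summarized as frequency and percentages for each evaluation by severity (None, Mild, Moderate and Severe) at each visit".
- SAP 4.1: Tables 14.2.6.1 to 14.2.6.9 (ITT, PP and subgroups) all begin "Proportion of Subjects with Local Skin Reactions by Visit". The title of Table 14.3.3 (Safety Population) names no visit, but its content falls under 2.5.2.
- Protocol 11.5.2: the seven signs "will be summarized by visit".

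On data collection, Protocol 8.2 says "Local Reactions in the treatment area will be documented separately" and requires a severity and a start and stop date for every local reaction. It defines the severe grade by the subject stopping study product because of the reaction. The Study Schedule places the local tolerability evaluation at Visits 2 to 6. It has no column for early withdrawal.

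**The concern.** A reader of the endpoint expects one number per arm: how many subjects had a local skin reaction. Nothing listed produces it. No table counts a subject once, no rule derives a worst post-baseline grade, and no rule separates signs already present at Baseline from new or worsened ones, although the evaluation is also done at Baseline.

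The study objective is dose-response in safety as well as efficacy, and this is the named secondary endpoint for local safety. If reactions are short relative to the four-week visit spacing, by-visit rates can understate how many subjects react. If the timing of reactions differs between regimens, the understatement could differ by arm. The data for a better summary are already to be recorded, but the SAP does not say how they are used.

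**Working it through.** The documents state no rate, duration or precision for endpoint 7, so there is no plan figure to reproduce. Two checks apply.

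**1. Can by-visit rates give the subject-level proportion?**

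Inputs: four post-baseline visits (Weeks 4, 8, 12 and 16) and 60 subjects per arm, both from the Protocol. A rate of 20% at each visit, with all subjects assessed, is assumed for illustration.

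- Affected at each visit: 0.20 × 60 = 12.
- Lower bound, the same subjects every time: 12 of 60 = 20%.
- Upper bound, different subjects every time: 4 × 12 = 48 of 60 = 80%.

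The same four by-visit rows fit any value from 20% to 80%. This holds whether by visit means status on the day or status since the last visit.

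**2. How much could be missed if by visit means status on the visit day?**

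Inputs: 84 treatment days and nominal visits at Days 28, 56, 84 and 112, from the Protocol. Assumptions: one episode per affected subject, lasting D days, with onset uniform over the 84 days.

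For D up to 28, the episode covers a visit day only if it starts in the D days up to Day 28, 56 or 84. The chance is therefore 3D/84 = D/28.

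| Duration D (days) | Chance of being present at a visit |
|---|---|
| 3 | 3/28 = 11% |
| 5 | 5/28 = 18% |
| 7 | 7/28 = 25% |
| 10 | 10/28 = 36% |
| 14 | 14/28 = 50% |
| 21 | 21/28 = 75% |
| 28 or more | 100% |

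Example: suppose 30 of 60 subjects in an arm each have one reaction.

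- At 7 days, the tables would show 30 × 0.25 = 7.5 subjects across all visits, or 7.5/3 = 2.5 at each on-treatment visit.
- At 14 days, they would show 30 × 0.50 = 15 subjects, or 15/3 = 5 at each on-treatment visit.
- A count from the recorded dates would show 30 in both cases.

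Two qualifications apply. With ±5-day windows at both ends, the gap between post-baseline visits can run from 18 to 38 days, so the 28-day threshold is nominal. Recurrent or persistent reactions would be seen more often than the table shows.

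**The case against.** **By visit is a legitimate reading of the endpoint.** SAP 2.6 and Protocol 11.4 set the secondary product comparisons at Visits 3 to 6, and Tables 14.2.6.1 to 14.2.6.9 do give proportions of subjects with reactions at visits. A reader might infer that endpoint 7 is never computed. The documents do not support that: it is computed visit by visit. What is missing is the proportion over the study, which the endpoint's wording, with no week named, most naturally asks for.

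**Reactions between visits may still be captured.** A reader might infer that only visit-day status is tabulated and that reactions clearing between visits are never counted. Both are inferences. The SAP does not define by visit, and the table shells are in a separate file that is not available here. Between-visit episodes may appear in Listing 16.2.9.1, or in the AE tables if also recorded as AEs, although Protocol 8.2 makes the second route uncertain by documenting local reactions apart. Neither route is specified to give an any-time proportion.

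**Early withdrawal is not a special omission.** The list in Protocol 7.10.7 has no local tolerability step, and the severe grade is tied to stopping product, so a reader might infer that severe reactions drop out of the tables. But none of the lists for Visits 2 to 6 (7.10.2 to 7.10.6) names the evaluation either. Section 7.10.7 does include AE collection with diary review and a skin examination, and Protocol 7.6 asks for the End of Study evaluations where possible. The rule against imputing missing safety data belongs to the Safety Population, whereas Tables 14.2.6.1 to 14.2.6.9 are ITT and PP tables. SAP 2.1 applies LOCF and multiple imputation where no other method is defined, and the titles of these tables name neither. How withdrawn subjects enter them is unsettled.

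**The size is assumed.** Cream is applied twice daily for 12 weeks in every arm, so persistent irritation is plausible, and at nominal spacing nothing lasting 28 days or more is missed. A reader might also infer that local reactions are the main expected difference between regimens. The documents do not say so: Protocol Section 1 attributes the skin findings in both animal studies to the vehicle or to constituents other than celecoxib. Bias between arms is possible but not shown.

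**Conclusion.** The point holds in a limited form. Endpoint 7 has only by-visit tables. The SAP defines neither an any-time proportion of subjects nor a worst post-baseline grade, and it states no use for the dates and severities collected under Protocol 8.2.

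That by-visit rates cannot be converted into the missing proportion is arithmetic and needs no assumption about reactions. The possible understatement is conditional. It requires by visit to mean visit-day status, which is the natural but undefined reading, and reactions shorter than about four weeks. Under a single episode with uniform onset, the share missed is 75% at 7 days, 50% at 14, 25% at 21 and none at 28 or more.

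The primary endpoint, sample size and error rate are unaffected. The gap is in the analysis plan rather than clearly in data collection. The change is worth making because a named secondary endpoint otherwise lacks its most direct summary and the remedy is cheap.

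**What to change.** 1. In SAP 2.5.2, and in Tables 14.2.6.1, 14.2.6.2 and 14.3.3, add per-subject rows by treatment group, for each of the seven signs and for any sign. They should give (a) any local reaction new or worse than Baseline from first application through Week 16 and (b) the worst post-baseline grade. Derive them from the visit assessments plus the recorded severity and dates, including early-withdrawal records.
2. Name these rows as the analysis of endpoint 7 and keep the by-visit tables as supportive.
3. Show alongside them a version using only investigator-observed visit assessments, so that the contribution of between-visit records is visible.
4. Define by visit (status on the day, or since the last visit) and state how missing assessments and withdrawn subjects are handled in Tables 14.2.6.1 to 14.2.6.9.
5. Reconcile the procedure lists in Protocol 7.10.2 to 7.10.7, none of which names the local tolerability evaluation, with the Study Schedule, which has it at Visits 2 to 6 but has no early-withdrawal column. Changing 7.10.7 alone would leave the other five lists inconsistent.

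Cost: a few extra table rows from data already to be collected, and a tidying of the lists. The reported reaction rates may be higher, and some between-visit episodes may rest partly on subject recall, which is why item 3 is included.
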